## Research Protocol/Protocol Addendum Template

---

Additionally, the population that we will recruit for this study are also at higher risk for substance misuse because these are very common conditions among patients who are treated in acute inpatient or residential treatment settings. Therefore, we will treat substance misuse (e.g., alcohol use disorder) as well as admission to a detox facility as anticipated adverse events. Related to these concerns, we also expect that patients may be incarcerated, especially due to drug use, while participating in the study. We will capture this as an adverse event, and we will consider it to be anticipated, particularly if related to drug or alcohol use. No study-related procedures will be conducted while a patient is incarcerated. Participants may choose to continue with the study upon their release, under the discretion of [name]. [name] will determine together with the study staff whether the patient needs to be reconsented prior to continuing in the study. If any study visits occurs when the patient is incarcerated, the visit will be captured as "missed" (i.e., that particular visit will be skipped).

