### **Project Proposal, Phase 3, Aim 3**

To test our hypotheses as described above, we propose to conduct an assessor - blinded RCT comparing the BESST intervention plus standard care to standard care alone. We will enroll up to 25 patients who are 18 years or older and are being discharged from a VA-CCN mental health treatment setting. The primary aim is to determine whether the BESST intervention reduces suicidal ideation at one and three months after discharge. The secondary aim is to evaluate the impact of the BESST intervention on other related measures of suicide risk including hopelessness, social connectedness, fatal/non-fatal suicide attempts and treatment engagement.

**Randomization:** Prior to the start of study enrollment, the study team otherwise not involved in recruitment will independently prepare allocation cards using a permuted block schedule. The same study staff member will then put these prepared allocation cards into sealed, opaque, numbered envelopes. After obtaining consent and completing the baseline assessment (see description below), the study staff member will take the next numbered envelope from the box (described above) and open the envelope to determine the patient's assignment. In the event that the patient has been assigned to the intervention, the study staff will notify the intervention staff in order that the intervention staff can initiate the intervention. Otherwise, the patient will be informed that they have been assigned to usual care.

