**Baseline Characteristics:** We will collect socio-demographic data from the electronic medical record such as age, sex, marital status and service history (e.g., branch, era, combat exposure). We will also collect diagnostic information using either the MINI International Neuropsychiatric Interview (MINI), which has been validated against the Structured Clinical Interview for Diagnostic and Statistical Manual of Mental Disorders (DSM). The MINI is a short, structured diagnostic interview that, on average, takes about 15 minutes to administer. We will ask about any history of suicide attempts using the validated Columbia Suicide Severity Rating-Scale (C-SSRS). The C-SSRS includes a seven-item subscale that assesses for actual and interrupted suicide attempts.

**Primary Outcome (Suicidal Ideation):** The primary outcome will be assessed using the Beck Scale for Suicidal Ideation (BSS) (Specific Aim 1). Patients will be asked about their current suicidal ideation (i.e., past week) at baseline and at the one-month and three-month follow-up

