## Research Protocol/Protocol Addendum Template

---

secondary aims of interest of this study. We will assess for statistically significant differences in baseline study characteristics such as age, sex, race, and mental health diagnosis, between study arms using *t*-tests for continuous measures and chi-squared tests for dichotomous variables. We will report these results using 95% confidence intervals (CI) and *P*-values. We will define statistical significance as a *P*-value < 0.05.

**Specific Aim 1:** We will generate descriptive summary statistics (e.g., means and standard errors, medians) and graphical displays for the BSS total scores at baseline and at each of the follow-up assessments. In the case of the pilot study of the BESST intervention in up to six patients, we will use a repeated measures analysis of variance (ANOVA) test to assess for changes in continuous variables in the first three months after discharge. Second, if the repeated measures ANOVA suggested a significant difference in means across time, we will perform a post-hoc, pair-wise comparison of means at baseline and at each follow-up using a two-sample *t*-test.

With regards to the RCT of the BESST intervention, we will use a generalized linear mixed model to assess for changes in continuous variables in the first three months after discharge. We will consider allocation of study arm (categorical measure) and time (continuous measure) as fixed effects. Random effect will be used to account for correlation that arises from repeated measures of the same individual. We will assume a linear effect and model changes in suicidal ideation over time. We will calculate 95% CI and *P*-values and will define a *P*-value of < 0.05 to be statistically significant. We will use the maximum likelihood ratio to account for any missing data. Based on available evidence, we hypothesize that the BESST intervention plus standard care will lead to a significant reduction in suicidal ideation after discharge.

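### Outcome assessments that fall during incarceration are skipped rather than deferred until release, which gives up obtainable one- and three-month data

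*Combined protocol and SAP*

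**What the plan says.** The rule is in Risks and Side Effects, under Potential Risks. The protocol says "we also expect that patients may be incarcerated, especially due to drug use, while participating in the study". It then states: "No study-related procedures will be conducted while a patient is incarcerated". It adds: "Participants may choose to continue with the study upon their release", subject to discretion and, if judged necessary, reconsent. A study visit that occurs in custody is to be recorded as missed, which the protocol explains as "that particular visit will be skipped". The rule covers study visits of every kind, so it reaches the outcome assessments as well as the education session and the contacts.

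Several other sections bear on it:

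- Project Proposal, Phase 3, Aim 3: "The primary aim is to determine whether the BESST intervention reduces suicidal ideation at one and three months after discharge".
- Table 2 schedules the BSS, the C-SSRS and the substance-use timeline follow-back at baseline, one month and three months. Protected Health Information adds self-reported non-VA care at the two follow-ups.
- Study Design allows follow-up by telephone, by VA Video Connect or in person.
- Statistical Analyses, Specific Aim 1, fits a mixed model with continuous time. Its only provision for gaps is: "We will use the maximum likelihood ratio to account for any missing data". Specific Aim 2 repeats it.
- Reasons for stopping assigned treatment and follow-up lists only death and the patient's own request.

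**The concern.** Not assessing patients in custody is sound and agrees with the exclusion of prisoners. The difficulty comes after release. The patient may be back in the study, reachable by telephone and still owed follow-up under intention to treat, yet the rule as written does not call for the assessment to be made up.

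There are only two post-baseline assessments, so one skipped visit is half of a patient's follow-up. If it is the three-month visit, continuing in the study yields no final BSS. The same visit carries the C-SSRS report of attempts, which is summarised only as event counts and so gets no help from a model. It also carries the substance-use record and the report of non-VA care.

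The likelihood analysis is valid if missingness can be explained by what is observed and modelled. The protocol ties incarceration mainly to drug use, which is not a term in the BSS model, and the plan states no sensitivity analysis. If those affected also had different BSS scores and were spread unevenly across the arms, the estimated effect would shift.

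**Working it through.** The plan gives no incarceration rate, dropout rate or SD, so it has no figure of its own to reproduce here. The inputs from the documents are: up to 25 patients (Project Proposal, Phase 3, Aim 3), assessments at baseline, one and three months (Table 2), and 5 BSS points as the meaningful change (Sample Size). The allocation ratio is not stated; 12/13 is assumed.

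**1. Loss per skipped assessment.** 1/25 = 4% of the data at that time point. Within an arm, 1/13 to 1/12 = 7.7% to 8.3%, about 8%. Within the patient, 1/2 of post-baseline assessments.

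**2. Chance that the rule is used at a given visit.** With an assumed probability p of being in custody at the visit, P(at least one) = 1 − (1 − p)^25:

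- p = 2%: 0.5 patients expected, probability 40%
- p = 5%: 1.25 expected, 72%
- p = 10%: 2.5 expected, 93%

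**3. Possible shift in one arm's observed mean.** If k of 12 patients are skipped and would have scored d points worse than those observed, the shift is (k/12) × d, before any help from their other visits. For d = 5 to 10 (assumed), one patient gives 0.4 to 0.8 points and two give 0.8 to 1.7 points, against the 5-point benchmark.

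**4. Precision.** Assume SD 6, a two-sided 5% test and a 5-point difference. Then SE = 6 × √(1/12 + 1/13) = 2.40, 5/2.40 = 2.08, and power is about Φ(2.08 − 1.96) = 55%. With one patient lost from each arm, SE = 6 × √(1/11 + 1/12) = 2.50 and power is about 52%.

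**5. Skipping against late assessment.** Illustrative simulation, 200 trials per row: 13 control and 12 intervention patients, SD 6, within-patient correlation 0.5, true three-month effect −5, and affected patients 8 points worse at three months. The model was a random-intercept mixed model fitted by maximum likelihood, with an arm-by-time term that the plan does not list. The late assessment carries the same score, entered at month 4. Mean estimated three-month effect:

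| Affected: control / intervention | Complete data | Skipped | Late, at actual date |
|---|---|---|---|
| 1 / 1 | −4.8 | −4.9 | −4.6 |
| 2 / 0 | −6.5 | −5.2 | −7.1 |
| 0 / 2 | −3.6 | −5.0 | −2.6 |
| 3 / 1 | −6.6 | −5.3 | −6.7 |

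When the arms are equally affected, skipping changes almost nothing. In the three uneven rows it moves the estimate by 1.3 to 1.4 points, in a direction that depends on which arm is hit. Late assessment misses by 0.1 to 1.0 points in those rows and by 0.2 in the even one. The model's standard error is about 2.4 throughout, so all of these shifts are smaller than the uncertainty of a single trial.

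**The case against.** The case against is substantial.

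- The rule removes nothing that has been collected. Baseline and any other BSS stay in the mixed model, the incarceration is recorded as an adverse event, and VA utilisation still comes from the medical record. This stands: the loss is of data never gathered.
- Permanent loss partly rests on silence. The available text gives only nominal one- and three-month points, the schedule figure is not shown, and the Assessment Manual is not in the file. A team might simply book the assessment just after release. That is possible, but the instruction as written is to skip the visit, and practice should not depend on staff reading around it.
- No section says that incarcerated patients have worse suicidal ideation. The stated link is to drug use, and only as the main reason. This stands; the worse scores in the working are assumed.
- A reader might infer that up to a quarter of one arm's three-month data could go (3/12). That requires three patients in custody at that visit, all in one arm. Three patients taken at random fall in one arm with probability (286 + 220)/2,300 = 22%, and nothing in the documents supports three cases at all.
- Deferral is not a clean repair. Section Primary Outcome says: "Patients will be asked about their current suicidal ideation (i.e., past week) at baseline", and the follow-ups use the same recall. A late score therefore describes a later week, possibly beyond the three months being modelled. This also stands, and it is why the fix needs a limit and a sensitivity analysis.

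**Conclusion.** The point holds as a modest, cheap improvement. Followed as written, the rule forgoes one- and three-month data that could be obtained from patients who return, at 4% of a time point per skipped assessment with 25 patients. How often this would happen is unknown.

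A reader might go further and infer that the rule selectively strips out deteriorating patients and so biases the trial. The documents do not support that. Bias in the arm comparison needs unequal incarceration, or unequal severity among those affected, and neither is documented. The simulated shifts of 1.3 to 1.4 points rest on assumed scores 8 points worse and an assumed uneven split. With an even split the effect is negligible.

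What remains does not depend on those assumptions: a late score at a known date can be analysed or set aside, whereas a score never collected leaves no choice.

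**What to change.** Keep the ban on study procedures in custody. For the one- and three-month outcome assessments only, replace skipping with deferral:

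- If the patient is released, chooses to continue and is reconsented where required, complete the assessment by telephone or VA Video Connect as soon as possible.
- State the normal visit window and an outer limit for deferred assessments. The one-month limit should close well before the three-month visit.
- Record the actual date and use it as the time value in the mixed model, which already treats time as continuous.
- Record the assessment as missed only when the outer limit has passed, with incarceration as the reason and by arm.
- Add one sensitivity analysis that leaves out assessments made outside the normal window, and report it beside the main result.

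The cost is a sentence or two in Potential Risks, a stated window, and one further model fit. No assessment is added to those already planned. The downside is that a few BSS scores will reflect a later week than the nominal one- or three-month point.

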### ***Therapeutic Risks***

During the study, the research staff will ask patients questions about how they are feeling and their interactions with other people. Patients will be exposed to these therapeutic risks during the baseline and each follow-up assessment. In addition, patients who receive the intervention condition will also be exposed to these therapeutic risks at the intervention visits (brief education visit plus seven contact visits after discharge). In some cases, patients can feel embarrassed, nervous, bored, or generally uncomfortable when they are asked to answer these types of questions. However, because we have sufficient safeguards in place to mitigate these potential risks, we believe that the overall therapeutic risk from this study to enrolled patients is very low.

### ***Research Risk***

During the course of the study, we will collect from enrolled patients protected health information including name, social security numbers (in order to process participant payments), phone numbers (for contact purposes), sociodemographic information (e.g. age, race), psychiatric diagnoses (e.g. Alcohol Use Disorder, Substance Use Disorder, Depression), mental health treatments received, and psychiatric symptoms (e.g. responses to standardized questionnaires). Therefore, there is some risk that a patient's confidentiality or protected health information could be compromised due to study participation. As we have sufficient safeguards in place to mitigate this risk (see Protection Against Risk below), we believe the overall research risk in this study is very low. We will also make every effort to conduct study-related procedures in a private setting.

### ***Protection Against Risk***

#### *Study Population Safety Risk*

At each study assessment time point (i.e., baseline and one-month, and three-month follow-up), patients will be assessed for symptoms of suicidal ideation and suicidal behavior because these are *a priori* study endpoints. In addition, for patients receiving the intervention, patients may report worsening suicidal ideation or suicidal behavior in the context of the intervention visits. Regardless of whether the patient is receiving the intervention or is assigned to usual care alone, the study staff will be ethically bound to take appropriate action if the patient is at imminent risk for self-harm. The Safety Alert Protocol outlines the process that study staff members will take in order to ensure the safety and well-being of all enrolled patients regardless of whether they are receiving the intervention or usual care alone. In the case that a safety alert is met, the research staff member will contact [name] (or the mental health physician covering for her) or, if necessary, the patient's mental health provider. As part of this risk assessment, the assessing clinician will immediately complete a comprehensive evaluation of

## Research Protocol/Protocol Addendum Template

---

the patient's risk and determine the most appropriate next level of care for the enrolled patient. The next level of care may include psychiatric admission, emergency room referral, or an outpatient follow-up with the patient's healthcare provider. Please see the **Safety Alert Protocol** for a full description of all safety alerts and required actions by study staff members.

### *Therapeutic Risk*

Patients will be given sufficient time to answer questions and complete visits in order to reduce any discomfort they may experience as part of being enrolled in the study. Patients will also be made aware that if any of the questions make them feel uncomfortable, they should feel free to report this to the study staff member and have this concern addressed immediately. At any point during a study visit, a patient can take a break or refuse to answer a question.

### *Research Risk*

Every effort will be made to ensure that we maintain the privacy and confidentiality of the patient. All in-person, study visits will occur in a private office on the WRJ VAMC campus to ensure privacy. If a visit or assessment is done via a phone call, the research staff will conduct the phone call in a private office. All assessments that can be collected electronically will be stored on a secure, password-protected file on a secure, local researcher server. All staff associated with the study will complete required security training prior to the start of the study in order to be permitted access to this server. Furthermore, all study staff will adhere to the required annual training (by the WRJ VAMC) necessary to maintain their access to the server. All paper copies of study-related data, including consent and HIPAA forms, will be kept in a locked file cabinet, in a locked office, dedicated to this study. Only the research staff will have access to this locked cabinet.

### **Benefits:**

All of the patients who participate in this study will receive standard of care and will be able to continue all treatments and mental health care that they would otherwise have access to outside of the study. In addition, some patients may receive the intervention in addition to standard care. The intervention is designed to enhance care that patients receive by helping to connect them with available mental health resources and educating them about suicide prevention after discharge. Although the intervention is adapted from a successful suicide prevention strategy (WHO BIC) and has also been studied in VA treatment settings, it is unknown whether the intervention significantly reduces suicide risk after discharge relative to standard discharge practices in patients who access VA-contracted community care inpatient or residential treatment. The work from this proposed study will be able to more definitively address whether the intervention is an effective suicide-prevention strategy in patients who access VA-contracted community care inpatient or residential treatment. This is important, given that suicide remains an important problem in the Veteran population. Because the overall risks associated with this study are minimal and the anticipated benefits and knowledge to be gained are clinically relevant, there is sufficient reason to conduct this proposed study.

### **Protected Health Information:**

We will administer several validated instruments to all enrolled patients at baseline and follow-up (one- and three-month follow-ups). These instruments ask various questions related to self-harming thoughts or behavior and social connectedness. We will also ask patients to report on any non-VA healthcare utilization at one- and three-month follow-ups. Demographic data and other baseline characteristics will be collected from the patient's electronic medical record at baseline. Information on VA healthcare utilization will be

### **Resources Available**

[name] will oversee and lead this project with the help of research staff, which includes:

- An interventionist (75% Year 2)
- A research coordinator (50% Year 2)
- A study assessor (75% Year 2)
- Administrative support (25% Year 2)

### **Subject Compensation:**

We will compensate enrolled patients as follows: baseline: \$100; one-month follow-up: \$100; and three-month follow-up: \$100. We chose this payment schedule so that patients are sufficiently reimbursed for their time and effort in the study. We will make every effort to compensate participants, however, if a participant refuses payment or does not provide the required information for payment purposes, study staff will pursue the following process: In the event that the patient has completed all assessments and/or interventions, and still has not provided the required information to pay them, the study staff will make reasonable efforts to obtain the information from the patient. If the patient still does not provide the required information to be paid, we will classify this patient as "unable to be paid".

### **Privacy and Confidentiality:**

Please see *Protection Against Risk* above.

### **Data and Safety Monitoring Plan**

**Monitoring and Interim Analysis Plan:** We will seek oversight for the RCT portion of our proposal. Specifically, we will request that the Dartmouth Data Monitoring Committee (DSMB). The DSMB will meet annually. The DSMB will focus on ensuring safety and feasibility, including participant accrual and retention, adverse events monitoring, and data analyses. Based on these findings, the DSMB may recommend: (1) continued approval (unconditionally or with conditions to be addressed); (2) probation; or (3) possibly termination, if there are problems with enrollment or safety concerns.

### **Study Safety & Monitoring:**

Enrolled patients will be monitored for any unanticipated problems or adverse events during the course of the study. Unanticipated death possibly related to research will be orally reported to VINNE immediately with a written report submitted via IRBNet within 5 business days. Possibly study-related unanticipated problems involving risk to subjects or others; serious adverse events; and deviations/non-compliance will be reported within 5 business days to VINNE.

